Study Protocol

Title: Value of Glycated Albumin in Intervention of Glycemic Control in Patients with Type 2 Diabetes: A Multicenter, Randomized Controlled Clinical Study

NCT No.: NCT05227677

VERSION: 2.0

DATE: December 28, 2021

1. Research Background and Rationale for the Study

With the aging population and changes in lifestyle in China, diabetes has evolved from a rare disease to a widespread epidemic. The prevalence of diabetes surged from 0.67% in 1980 to 11.2% in 2017 [1]. As research into the disease has deepened, treatment options for diabetes have expanded significantly. However, previous studies have shown that only 35% of patients treated with oral antidiabetic drugs (OADs) alone and 26% of those treated with OADs combined with insulin achieved the target glycated hemoglobin A1c (HbA1c) level of <7% [2]. Inappropriate treatment choices may be a major factor contributing to poor glycemic control. Therefore, identifying clinical biomarkers to adjust and evaluate treatment efficacy is a crucial step in personalized diabetes management.

Currently, HbA1c and self-monitoring of blood glucose (SMBG) are commonly used clinical indicators for adjusting glycemic control. HbA1c is recommended by both international and domestic guidelines as the gold standard for assessing glycemic control [3–5]. Although HbA1c reflects the average blood glucose level over the past 2–3 months and serves as a reliable indicator of diabetes control, it is susceptible to interference from age, abnormal hemoglobin, and certain conditions such as hemolytic anemia and normal pregnancy, which accelerate red blood cell turnover and affect HbA1c measurements. For patients undergoing treatment adjustments or newly diagnosed with diabetes, HbA1c cannot promptly reflect recent changes in glycemic control. While SMBG provides real-time glucose readings, a recent randomized controlled trial published in JAMA showed that SMBG does not improve glycemic control in non-insulin-treated type 2 diabetes patients [6].

In recent years, glycated albumin (GA) has emerged as a promising biomarker for glycemic control and treatment adjustment in diabetes [7–10]. Studies have shown that GA has a half-life of 17–19 days, allowing it to reflect the average blood glucose level over the past 2–3 weeks and recent changes in glucose levels, without being affected by age, gender, diet, medications, or glucose fluctuations—thus addressing the limitations of HbA1c [11]. Recent short-term studies have found that changes in GA can predict changes in HbA1c levels three months later in newly diagnosed type 2 diabetes patients and those undergoing treatment adjustments [8]. Furthermore, preliminary results from a pilot study conducted for this research showed that patients whose treatment was adjusted based on GA had an HbA1c target achievement rate (<7%) of 76.9% after three months of follow-up, compared to 46.2% in the control group. Similarly, the achievement rate for HbA1c <6.5% was 30.8% in the GA-adjusted group versus 23.1% in the control group. Therefore, our research hypothesis is that adjusting

treatment based on GA results is more beneficial for improving patients' average blood glucose levels (HbA1c).

2. Research Objective

To validate the hypothesis that "adjusting treatment regimens based on glycated albumin (GA) test results is more effective in helping patients achieve target average blood glucose levels (HbA1c)."

3. Research Methods and Design

3.1 Study Population, Inclusion Criteria, Exclusion Criteria, and Withdrawal Criteria

3.1.1 Study Population:

A total of 200 newly diagnosed type 2 diabetes patients will be enrolled based on the 1999 WHO diagnostic criteria.

3.1.2 Inclusion Criteria:

- 3.1.2.1 Patients voluntarily signed informed consent forms;
- 3.1.2.2 Age between 20 and 70 years;
- 3.1.2.3 Newly diagnosed type 2 diabetes patients with a disease duration of less than 1 year and no use of antidiabetic medications in the past 3 months; HbA1c ≥7.5% and <10.5%;

3.1.3 Exclusion criteria:

- 3.1.3.1 Presence of proliferative retinopathy or macular degeneration requiring treatment, painful diabetic neuropathy, diabetic foot, diabetic ketoacidosis, or hyperglycemic hyperosmolar state within the past 3 months;
- 3.1.3.2 History or presence of the following conditions within the past 6 months:
 - 1) Decompensated heart failure (NYHA class III or IV);
 - 2) Myocardial infarction, coronary artery bypass grafting, or coronary artery stent implantation; 3) Uncontrolled severe arrhythmia, and deemed unsuitable for participation in this clinical trial by the investigator;
 - 4) Hemorrhagic stroke or ischemic stroke, and deemed unsuitable for participation in this clinical trial by the investigator;
- 3.1.3.3 Laboratory test results meet any of the following criteria:
 - 1) Alanine transaminase (ALT) or aspartate transaminase (AST) > 3 times the upper limit of normal;

- 2) Total bilirubin > 2 times the upper limit of normal;
- 3) Hemoglobin < 100 g/L;
- 4) Total protein < 60 g/L;
- 5) Albumin < 30 g/L;
- 6) Estimated glomerular filtration rate (eGFR) <60 mL/min/1.73 m²;
- 3.1.3.4 Any condition that may cause red blood cell instability and affect HbA1c testing, such as thalassemia or hemolytic anemia;
- 3.1.3.5 Currently has uncontrolled thyroid dysfunction;
- 3.1.3.6 Has received systemic steroid therapy within the past month (excluding inhaled or topical use);
- 3.1.3.7 Pregnant or lactating women;
- 3.1.3.8 Two or more episodes of severe hypoglycemia within the past year prior to screening;
- 3.1.3.9 Patients whom the investigator deems require initiation of sulfonylurea, glinide, insulin, or insulin analog therapy;
- 3.3.3.10 Patients currently receiving calcium hydroxybutyrate treatment or with a condition requiring calcium hydroxybutyrate treatment, and who the investigator believes may require additional calcium hydroxybutyrate treatment in the near future.
- 3.1.3.11 The investigator deems the subject unsuitable for observation.

3.1.4 Withdrawal criteria:

3.1.4.1 Withdrawal decided by the investigator

The investigator may decide to withdraw a subject from the study under the following circumstances:

- 1) Safety concerns arise, and the investigator believes that continuing the study may compromise the subject's safety;
- 2) Serious complications or adverse events occur during the study, rendering the subject unsuitable for continued participation;
- 3) Poor compliance by the subject or severe non-adherence to study procedures, which may affect safety or efficacy evaluation;
- 3.1.4.2 Subject withdrawal

Subjects may withdraw from the study at any time. Subjects may freely terminate study participation at any time without affecting further treatment. Study completion or termination should be documented in the CRF, along with all reasons for termination. Possible reasons for subject withdrawal from the study include:

- 1) Withdrawal of informed consent by the participant;
- 2) Loss to follow-up (at least three documented attempts to contact the participant must have been made prior to loss to follow-up);
- 3) Other circumstances leading to withdrawal from the study (e.g., change of residence rendering continued medication and follow-up impossible).

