3.3.4 Visit 3B - Follow-up Period (Visit 3A + 5 days)

- *Preferably within 3 days after Visit 3A, with a maximum of 5 days.
 - 3.3.4.1 Patients in Group B will not participate in this follow-up visit.
 - 3.3.4.2 Patients in Group A will undergo a physical examination (measurements: weight, waist circumference, blood pressure, pulse rate). The GA results for Group A patients will be communicated to the study physician and the patients. The study physician will adjust the medication based on the GA results.

Drug adjustments follow the "GA normalization" principle: if GA > 16%, the study physician increases the type of oral medication based on the 2020 Chinese Diabetes Prevention and Control Guidelines (Figure 2). Due to the risk of hypoglycemia, sulfonylureas, glinides, insulin, or insulin analogues are prohibited in this study. If $GA \le 16\%$, no drug adjustments are made. However, if a patient reports hypoglycemia within the past month, the cause of hypoglycemia must be identified first and appropriate management provided. Since this study excludes sulfonylureas, glinides, insulin, or insulin analogues, the theoretical risk of hypoglycemia is extremely low. If unexplained hypoglycemia occurs, the investigator may consider reducing the dose of oral hypoglycemic agents as appropriate.

3.3.4.3 Record all data (medication status, occurrence of hypoglycemia, and other adverse events).

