4.1. Efficacy Endpoints

4.1.1. Primary Endpoints

Proportion of subjects achieving HbA1c < 7% at Visit 5 (Week 12 ± 3 days)

Percentage of subjects == (Number of subjects with HbA1c < 7%) / (Total number in efficacy analysis set) × 100%

The efficacy analysis set includes:

- Full Analysis Set (FAS)
- Per Protocol Set (PPS)

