4.5. Protocol Deviations and Medication Adherence

Protocol Deviation: Clinical trials must adhere to GCP principles and comply with the trial protocol approved by the Ethics Committee. Any intentional or unintentional deviation from or violation of GCP principles and the trial protocol is referred to as protocol deviation or protocol violation.

Medication Adherence: The CRF collects information on the participant's medication adherence since the last visit, including whether antidiabetic medications were taken as scheduled (never missed, rarely missed [no more than 3 times per week], frequently missed [3 or more times per week], almost never taken, or taken in excess), whether antidiabetic medications were missed or taken in excess since the last visit, the medication name, administration details, and the total missed/overdose total dose, and unit of measurement.

5. Statistical assumptions

Not applicable.

6. Analysis data set

Randomized population: The entire population that received randomization is considered the randomized population.

Full analysis set (FAS): Participants who received randomization, met the study eligibility criteria, and had baseline measurements for the primary efficacy outcome. The FAS analysis follows the intention-to-treat (ITT) principle.

Per-protocol set (PPS): Participants in the FAS who demonstrated good compliance and had no important protocol deviations that affected the primary efficacy assessment (specific criteria will be confirmed during data verification).

Safety set (SS): All participants with at least one safety assessment are included in the safety analysis.

7. Statistical Methods

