7.2. Data processing methods

7.2.1. Advance withdrawl and missing data

All missing data will not be imputed.

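### An investigator may withdraw a randomised subject from the study for poor compliance, and nothing visible requires that subject's Visit 5 HbA1c, although the subject stays in the FAS

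*Protocol*

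**What the plan says.** Protocol 3.1.4.1 opens with "The investigator may decide to withdraw a subject from the study under the following circumstances", and its third item is "Poor compliance by the subject or severe non-adherence to study procedures, which may affect safety or efficacy evaluation". No threshold for poor compliance is given. On leaving the study, the protocol (3.1.4.2) asks only this: "Study completion or termination should be documented in the CRF, along with all reasons for termination". Table 1 and Protocol 3.3.6.2 place HbA1c at screening and at Visit 5 and nowhere between.

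The FAS (Protocol 5.1, SAP section 6) needs randomisation, eligibility and a baseline value of the primary efficacy measure. It does not need a Visit 5 value. Of this set the SAP says: "The FAS analysis follows the intention-to-treat (ITT) principle". Compliance enters through the PPS: "Participants in the FAS who demonstrated good compliance and had no important protocol deviations". SAP 7.3.6 tabulates adherence in the FAS, down to subjects who hardly ever took their medication.

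For the primary endpoint, SAP 4.1.1 divides by the "Total number in efficacy analysis set", while SAP 7.2.1 states: "All missing data will not be imputed".

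In Protocol 3.3.4 the study physician receives the GA result for Group A and acts on it, and of Visit 3B the protocol says: "Patients in Group B will not participate in this follow-up visit".

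**The concern.** The withdrawal is from the study and not only from treatment. A judgement made after randomisation can therefore end measurement of the one value that defines the primary endpoint. The person making that judgement knows the arm, because only Group A's GA result reaches the physician and only Group A attends Visit 3B. Neither document uses the words open-label or masked; this is inferred from the design.

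The analysis does not need such withdrawals, because poor compliers can already be set aside through the PPS. The FAS is meant to keep them, but it can only keep their names if their HbA1c is not taken. If the rule is used more in one arm than in the other, the primary comparison can shift, and no later analysis recovers a value that was never measured.

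**Working it through.** **What the documents fix.** The pilot rates are 76.9% and 46.2% (Protocol 3.5, SAP 3.3), a difference of 76.9 − 46.2 = 30.7 points. There are 100 subjects per arm. Pilot completion was 72.5%, so 100 × (1 − 0.725) = 27.5 per 100 did not complete, for any reason. The share due to poor compliance is not given, and the plan has no figure of its own for this point to reproduce.

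**Following one subject through the text.** A subject is randomised with a baseline HbA1c, complies poorly, and is withdrawn at week 8 under item 3. Under Protocol 5.1 and SAP section 6 the subject is in the FAS. Under Table 1 the only post-baseline HbA1c was due at week 12. The reason is recorded and no HbA1c exists.

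The effect then depends on how the missing value is treated, which SAP 4.1.1 and 7.2.1 leave open to two readings. The number withdrawn and their response rate are assumptions in both.

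**Reading 1: missing counts as not achieved (SAP 4.1.1 taken literally).** Assume 10 of 100 are withdrawn in Group A only, and let *q* be the share of those ten who would have reached HbA1c <7%. At the pilot rates, difference = (76.9 − 10*q*) − 46.2.

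| *q* | Group A (%) | Difference (points) |
|---|---|---|
| 0 | 76.9 | 30.7 |
| 0.20 | 74.9 | 28.7 |
| 0.769 | 69.2 | 23.0 |

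With the ten in Group B only, the range runs the other way: from 30.7 (none would have responded) to 76.9 − 0.9 × 46.2 = 35.3 (all at that arm's rate).

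**Reading 2: missing subjects are dropped.** Assume no true effect (46.2% in both arms), 10 withdrawn in Group A and none in Group B, and all ten non-responders.

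- Group A: 46.2 / 90 = 51.3%. Group B: 46.2 / 100 = 46.2%. Spurious difference: +5.1 points.
- Pooled rate: 92.4 / 190 = 48.6%. Null standard error: √[0.486 × 0.514 × (1/90 + 1/100)] = 0.0726. Unpooled standard error: √[0.513 × 0.487 / 90 + 0.462 × 0.538 / 100] = 0.0725.
- Two-sided rejection rate: Φ[(0.0513 − 1.96 × 0.0726) / 0.0725] + Φ[(−0.0513 − 1.96 × 0.0726) / 0.0725] ≈ 0.105 + 0.004 = 10.9%, against 5.0% with full follow-up.
- If the ten would have responded at 20%: (46.2 − 2.0) / 90 = 49.1%, a spurious +2.9 points. If at 46.2%, there is no bias.
- Equal withdrawal in both arms on these terms gives no bias under no effect.

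Excess withdrawal in Group A thus shrinks the difference or leaves it alone under Reading 1, and inflates it or leaves it alone under Reading 2.

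**The case against.** The strongest case on the other side is that the texts are compatible. Item 3 is permissive and limited to non-compliance that may affect safety or efficacy evaluation. A poor complier can be kept, measured, tabulated in the FAS and left out of the PPS; a withdrawn one also stays in the FAS. A reader might infer that item 3 contradicts the SAP. The documents do not support that. They leave a gap: outcome collection after withdrawal is not specified.

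A reader might also infer that the rule will act unequally, since Group A has an extra visit to miss. Unequal use is possible but not shown. The examination and recording that Group B has at Visit 3A take place for Group A at 3B, and nothing says that missing 3B leads to withdrawal.

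The 23.0-point figure also invites over-reading. It assumes that subjects withdrawn for poor compliance would have responded as often as the rest of their arm. They may well respond less often, and the range includes no change.

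There are partial safeguards. Reasons for termination must be recorded, and SAP 7.3.1 reports early withdrawals with reasons and summarises subject distribution by site, so heavy or uneven use could be seen. Seeing it does not restore the values.

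Finally, the withdrawal text reviewed is Version 2.0, whereas SAP section 1 cites Version 3.0. SAP 7.2.3, listed in the contents, was not in the text available for this review, though no data rule could supply an HbA1c that was never taken.

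What remains is that use of the rule before Visit 5, as written, loses the primary outcome of a subject whom the FAS retains.

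**Conclusion.** The point holds as a gap in outcome collection, with moderate confidence and subject to the Version 3.0 text. The protocol allows a discretionary withdrawal from the study, by someone who knows the arm, for a reason the PPS already handles, and asks for no HbA1c afterwards.

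The documents do not show that outcomes will be lost, that the arms will be treated differently, or which way the result would move. The illustrative range for ten withdrawals in Group A only runs from no change to a 7.7-point fall (30.7 − 23.0) if missing counts as not achieved. If missing subjects are dropped, it runs from no bias to about +5.1 points under no true effect, with two-sided alpha near 11%. Ten in one arm is an assumption, as are the response rates of those withdrawn. The 27.5% pilot non-completion shows that missing Visit 5 values are realistic here, but says nothing about how many would be due to item 3.

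**What to change.** Add to Protocol 3.1.4 that every randomised subject who has not withdrawn consent for follow-up, including any subject withdrawn by the investigator under 3.1.4.1, is asked to have the Visit 5 HbA1c at day 84 ± 3 and is analysed in the assigned arm. State alongside it that poor compliance by itself affects PPS membership only, and not collection of the outcome. First check whether Version 3.0 already says this.

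Item 3 need not be deleted. It also names safety evaluation, and the added text closes the gap without touching when a subject may be withdrawn.

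The cost is tracing some withdrawn or non-adherent subjects for a visit already on the schedule, and an amendment that needs Ethics Committee approval before use (Protocol section 7). The FAS effect may also look slightly smaller once non-adherent subjects are measured. No new procedure is needed.

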3.2 Study Population Grouping

Participants will be randomly assigned into two groups: the intervention group (Group A) and the control group (Group B), with 100 participants in each group. Randomization will be conducted using SAS software version 9.4 or higher, employing a block randomization method to generate a reproducible randomization table. Randomization will be implemented via sealed envelopes, assigning eligible participants to either Group A or Group B in a 1:1 ratio.

After randomization, physicians will prescribe antidiabetic medications according to standard clinical practice. The use of sulfonylureas, meglitinides, insulin, or insulin analogs is prohibited in this study due to the risk of hypoglycemia.

During the first month of follow-up, GA levels will be measured in Group A. Based on the principle of "GA normalization," physicians will adjust the treatment regimen accordingly (details in section 3.3.4.2). Blood samples will also be collected during the second and third months of follow-up for GA measurement, but these results will not be used to adjust treatment; they are solely for statistical analysis.

In Group B, blood samples will be collected at the same time points (1st, 2nd, and 3rd months) for GA measurement, but these results will also not be used for treatment adjustments and will be used only for statistical analysis.

3.3 Research steps and follow-up plan

The research steps and follow-up plan are shown in Figure 1 and Table 1.

[figure not shown]

Figure 1. Research process diagram

Table 1 Research flowchart

	Screening visits	Baseline [#]		Measurement of GA						
Visit number	1	2	3A	3B	4	5	Frozen sample			
visit time	Days	Day 0	4 weeks	4 weeks	8 weeks	12 weeks	Follow-up			
	-7 to 0		(baseline:	(follow-up	(baseline	(baseline	visit			
			$28 \pm 3 \text{ days}$	visit 3A + 5	56 ± 3	84 ± 3	completed			
				days) *	days)	days)				
informed consent	X									
Demographic	X									
information (name,										
gender, ethnicity, date										
of birth)										
Medical history ^a	X									
Physical examination	X		X^h	X^g	X	X				
b										
Collect samples and per	Collect samples and perform the following laboratory tests:									
Blood glucose-related tests	Xi					X				
С										
Complete blood count ^d	Xi					X				
Liver and kidney function	Xi					X				
е										
lipids ^f	Xi					X				
Blood or urine pregnancy	Xi									
test										
Blood sample	X		X^h		X					
collection (for GA										
measurement)										
Inclusion/exclusion	X	X								

criteria							
Confirm eligibility for		X					
enrollment							
Randomization		X					
Treatment plan		X					
Distribution of subject		X	X ^h	X ^g	X		
diaries							
Check and collect			X ^h	X ^g	X	X	
participants' report							
GA measurement			X ^g			X	
Adjust treatment plan			X ^h	X ^g	X		
Recording medication	X	X	X ^h	X ^g	X	X	
treatment							
Record and review		X	X ^h	X ^g	X	X	
(since the previous							
visit) (S) AE							
study termination						X	
Determination of GA							X
in frozen samples							

Notes:

#If screening and baseline are conducted on the same day, all duplicate steps need only be performed once

- *It is best to conduct the visit within 3 days after the 3A visit, with a maximum of 5 days
- a. Medical history includes information such as disease course and treatment methods
- b. Physical examination includes: height, weight, waist circumference, blood pressure, pulse (screening period); weight, waist circumference, blood pressure, pulse (follow-up period)
- c. Blood glucose-related tests include: fasting blood glucose, HbA1c, fasting C-peptide, fasting insulin
- d. Complete blood count: red blood cells (RBC), white blood cells (WBC), platelets (PLT), hemoglobin (HGB)
- e. Liver and kidney function: total bilirubin (Tbil), alanine transaminase (ALT), aspartate transaminase (AST), total protein (TP), albumin, blood urea nitrogen (BUN) or urea (Urea), serum creatinine (Cr), uric acid (UA)
- f. Lipid profile: Total cholesterol (TC), triglycerides (TG), low-density lipoprotein (LDL-C), high-density lipoprotein (HDL-C)
- g. Only for Group A participants
- h. Only for Group B participants
- i. If the patient has laboratory test results within the past 7 days, historical results may be used, and repeat testing is not required.

3.3.1 Visit 1 - Screening Period (Days -7 to 0)

- 3.3.1.1 Voluntarily sign an informed consent form;
- 3.3.1.2 Obtain demographic information (name, gender, ethnicity, date of birth);
- 3.3.1.3 Obtain relevant medical history information (disease course, treatment methods);
- 3.3.1.4 Physical examination (measurements: height, weight, waist circumference, blood pressure, pulse rate);
- 3.3.1.5 Collect samples and perform relevant tests: Blood glucose-related tests: fasting blood glucose, HbA1c, fasting C-peptide, fasting insulin; Complete blood count: red blood cells (RBC), white blood cells (WBC), platelets (PLT), hemoglobin (HGB); Liver and kidney function: total aminotransferase bilirubin (Tbil), alanine (ALT), aspartate aminotransferase (AST), total protein (TP), albumin, blood urea nitrogen (BUN) or urea, serum creatinine (Cr), uric acid (UA); Lipid profile: total cholesterol (TC), triglycerides (TG), low-density lipoprotein (LDL-C), high-density lipoprotein (HDL-C); Pregnancy test (blood or urine) for women of childbearing age. If the patient has laboratory test results within the past 7 days, historical results may be used, and repeat testing is not required. If any results are incomplete or certain indicators exceed 7 days, additional testing must be conducted during the screening period.
- 3.3.1.6 Blood draw and cryopreservation (to be measured at study completion for GA determination);
- 3.3.1.7 Initial review of inclusion/exclusion criteria.

